Self-reporting by patients was shown to be the most cost-effective in clinical and research settings[22]. However-being a subjective method-it also bears the highest risk of overestimating adherence compared to electronic measurements[23].

Observational retrospective studies based on dispensing data from pharmacy record database analyzed the refill adherence for different inhaled medication in asthma and COPD patients[24-26]. The importance of refill adherence is limited, since this measurement cannot assess the timing of the ingested or inhaled doses, which depends on the duration of drug action, and this has an important impact on the efficacy of treatment[27].

To investigate the variability in timing and taking adherence, measurements of dose and timing are necessary, which can be done with electronic medication monitors. Electronic monitoring provides precise data on the timing and pattern of inhaler actuation as well as detect multiple successive actuations (dumping)[28]. Electronic monitoring methods are non-invasive and represent one of the best ways to detect adherence patterns when using additional tools attached on the inhaler devices[29]. One of the electronic monitoring systems on the market are SmartInhaler™ devices (Adherium Ltd., Auckland, New Zealand), which have been validated for the assessment of adherence to inhaled medication on a daily basis[30]. The SmartInhaler™ devices are able to track time and date of each actuation of the inhaler device (incorporated switch activates by depression or rotation of the device) and

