transmit the data via a wireless connection to a secure web database[30]. This method of electronic monitoring has been used in several studies measuring adherence to inhaled medication[31, 32]. One study conducted with asthma patients using inhalative corticosteroids showed that the integrated audio-visual reminder function of these devices significantly improved adherence to inhaled medication[33]. For orally administered drugs or inhaled medications available as powder capsules, a new technology is used, which is called Polymedication Electronic Monitoring System (POEMS). This technology is composed of printed electronics, self-adhesive polymer film carrying loops of conductive wires that can be affixed to multidose punch card (Pharmis GmbH, Beinwil am See, Switzerland) with 28 cavities. Every time a powder capsule is taken out of the blister, a loop is broken leading to changes in electrical resistance that can be measured and recorded with date and time[34]. The reports generated by Smartinhalers and POEMS allow to detect whether the patients have taken the medication at the right time and dose.

INTERVENTIONS TO IMPROVE MEDICATION ADHERENCE

Maintenance of a sufficient adherence to the prescribed medication is of major importance for achieving a therapeutic success, particularly in chronic diseases. Haynes et al.[35] have reviewed randomized controlled intervention trials to improve the adherence to pharmacological regimens in patients with chronic diseases, including asthmatic patients. Both, adherence and clinical outcomes were measured in these studies. The authors found that less than 50% of the interventions achieved a significant improvement of adherence while only 30% demonstrated an improvement in clinical outcome. The best success was attained with interventions combining several intervention strategies (information, reminders, self-monitoring, reinforcement, counselling, telephone follow-up, supportive care, etc.). Interventions to improve medication adherence have had mixed results and successful interventions had been shown as usually complex[35].

STUDY OBJECTIVE

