Currently, no monitoring devices exist that were specifically developed for monitoring the adherence of the newly introduced inhalation-device Ellipta®. To assess adherence in patients undergoing treatment with Ellipta® a Smartinhaler with a placebo-device is handed out and patients are instructed to trigger a puff of the placebo every time when they inhale their active treatment. This procedure allows an indirect recording of date and time actuation of the Ellipta® inhaler.

For inhalation with powder capsules (Breezhaler and HandiHaler), POEMS are used. The capsules are pre-filled for the following 2 weeks with a patient's individualized prescription plan (mostly one time daily inhalation of capsule contents). The multidose punch cards are filled manually by a pharmacist. The participants with Breezhaler and HandiHaler will receive one multidose punch card for every 2 weeks. Every time the patients break a loop for taking the capsules, date and time are recorded on a microchip, which can be read when the patients bring back the empty punch card.

DATA COLLECTION AND OUTCOME MEASURES

The primary outcome of this study is “time to next asthma or COPD exacerbation”, defined as acute-onset worsening of the patient's condition beyond day-to-day variations requiring interaction with a health care provider[48], which may occur during the index exacerbation or follow-up. Data collections about this outcome are assessed after two, four and six months (number of exacerbations since last visit with exact period of exacerbation and number of exacerbation with hospitalization). If patients are not able to give information about the time of exacerbation, treating physician is contacted.

Sociodemographic variables such as gender, civil status, age, education level and employment status are obtained by a generic questionnaire at the baseline visit. Furthermore, body mass index (BMI), smoking status, as well as pack years (py) are assessed during this visit. In addition, disease-related questions such as allergies,

comorbidities, current medication and number of exacerbations in the previous twelve months are recorded including hospitalizations and emergency department attendance.

This project focuses on the implementation of a prescribed dosing regimen. Objective adherence will be analyzed according to the following widely used definitions[49]:

- Taking adherence: (Number of puffs inhaled during 24h/number of puffs prescribed during 24h) x 100.

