Statistical analyses, including descriptive statistic and survival analyses, are done using the software R (RStudio®, Boston, USA) and SPSS (IBM Corporation, Armonk, USA). Statistical significance is set at the 5% level. Time to next exacerbation is compared using the Kaplan-Meier method and Cox proportional hazard model. Results will be reported as HR (hazard ratio) with corresponding 95% confidence interval (CI) and p-value. A hazard ratio smaller than one is expected. This means that the intervention group will have a smaller risk for exacerbations. Associations between time to between exacerbation and independent predictors will be analyzed (taking adherence, timing adherence and gaps without

inhalation). Comparisons of secondary parameters are done using t-tests or chi-square-tests (or their nonparametric equivalents if continuous data are not normally distributed).

HANDLING OF MISSING DATA AND DROP OUTS

Patients will be rated as drop out when they will be excluded from the study at their request or if they will be no longer able to participate in the study until the final visit at six months. Patients, who will not be able to undergo all clinical examination during the follow-up visits, will remain in the study. Multiple imputation methods will be used to impute missing data with less than 25% missing values, which is typically more efficient than complete cases analysis when covariates have missing values[56].

ETHICS AND DISSEMINATION

This study is conducted according to the Helsinki Declaration and according to the good clinical practice guidelines. The study participation of the patients is voluntary and can be revoked at any time without specification of reasons and will have no disadvantages for their future medical care. The study was approved by the Ethics Committee of Nordwest- and Zentralschweiz (registry number: EK- 269/13) and was registered in the <https://clinicaltrials.gov/trials> database (NCT02386722). The results of this study will be disseminated via seminar and conference presentations and in academic peer reviewed journals.

DATA SECURITY/DISCLOSURE OF ORIGINAL DOCUMENTS

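### Ellipta adherence is recorded through an unvalidated placebo-puff proxy, and the analysis plan does not separate it from records taken on the treatment itself

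*Combined protocol and SAP*

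**What the plan says.** The section on measurement of objective adherence explains that "no monitoring devices exist that were specifically developed for monitoring the adherence of the newly introduced inhalation-device Ellipta". Users therefore receive a Smartinhaler fitted to a placebo device, and "patients are instructed to trigger a puff of the placebo every time when they inhale their active treatment". The plan is open about what this yields: "This procedure allows an indirect recording of date and time actuation of the Ellipta® inhaler".

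The other two recording routes are tied to the treatment. Smartinhaler devices "are able to track time and date of each actuation of the inhaler device" (section on medication adherence). For capsule inhalers, "Every time the patients break a loop for taking the capsules, date and time are recorded on a microchip".

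The section on data collection and outcome measures then gives a single set of definitions for taking adherence, timing adherence, gaps and maximal gap length, with no distinction by device. The statistical analysis section adds: "Associations between time to between exacerbation and independent predictors will be analyzed". The predictors it names are taking adherence, timing adherence and gaps. It contains no device term, stratum or sensitivity analysis, and no cross-check of the placebo record is described anywhere. The section on medication adherence makes a general claim with no exception for Ellipta: "The reports generated by Smartinhalers and POEMS allow to detect whether the patients have taken the medication at the right time and dose".

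**The concern.** For Ellipta, the numerator of taking adherence can come only from placebo puffs. The record shows whether the patient performed an added task on a second object, so it can be wrong in two ways:

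- **Omitted puff.** The dose is taken but no placebo puff is triggered. On a once-daily regimen with no other monitored inhaler, one omission counts as a missed dose, as a gap day, and as a recorded interval of about 2 × 24 = 48 h, outside the accepted 18 to 30 h.
- **False puff.** A placebo puff is triggered without the active dose, and the dose counts as taken.

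Measuring adherence is the primary aim in the abstract and part of the study objective, so these analyses carry weight even though the primary outcome is time to exacerbation. Treating physicians choose the inhaler, so device is not randomised. A shift in recorded adherence that belongs to one device enters the predictor analysis as if it were a difference in behaviour. As written, the plan gives no means of seeing whether the Ellipta records behave differently.

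**Working it through.** **The plan's own figures.** None bears on this point. The only design calculation (70 per group, hazard ratio 0.36, one-tailed 5%) concerns time to exacerbation and uses no adherence data. The documents give neither the Ellipta share nor any error rate for the placebo record, so everything below rests on assumptions.

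**Model.** Let *a* be a patient's true taking adherence, with assumed mean 0.803 and SD 0.140 (a Beta(5.7, 1.4) distribution), so variance V = 0.01954. Let *q* be the fraction of real doses accompanied by a placebo puff, independent of *a*, with mean m and SD s. Let *d* be the fraction of missed doses for which a placebo puff is triggered anyway. Recorded adherence is r = a·q + (1 − a)·d. In a linear approximation, the observed slope divided by the true slope is cov(a, r)/var(r).

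**Step 1: Ellipta users only, no false puffs (d = 0).**
mean r = 0.803·m; cov(a, r) = m·V; var(r) = (V + 0.803²)(s² + m²) − (0.803·m)².

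| m (s) | mean r | cov / var | slope factor |
|---|---|---|---|
| 0.95 (0.05) | 0.763 | 0.01857 / 0.01930 | 0.96 |
| 0.90 (0.10) | 0.723 | 0.01759 / 0.02247 | 0.78 |
| 0.80 (0.15) | 0.642 | 0.01563 / 0.02745 | 0.57 |

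**Step 2: all patients pooled.** Step 1 does not describe the planned analysis, which covers every patient. With Ellipta share f, the same true adherence in both groups, no error in the other records, and Δ = 0.803 − mean r:

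factor = [(1 − f)V + f·cov] / [(1 − f)V + f·var(r) + f(1 − f)Δ²].

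For f = 0.20 and m = 0.80, the numerator is 0.8 × 0.01954 + 0.2 × 0.01563 = 0.01876. The denominator is 0.01563 + 0.2 × 0.02745 + 0.16 × 0.1606² = 0.02525. The factor is 0.74.

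| m | 10% share | 20% share | 50% share |
|---|---|---|---|
| 0.95 | 0.99 | 0.98 | 0.96 |
| 0.90 | 0.95 | 0.91 | 0.82 |
| 0.80 | 0.85 | 0.74 | 0.59 |

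At a 10% share, overall mean adherence shifts by only −0.4, −0.8 and −1.6 points.

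**Step 3: false puffs (simulated).** With m = 0.95 and d = 0.10, the factor within Ellipta users is 1.05. With d = 0.20 it is 1.16, mean recorded adherence is 0.802 against a true 0.803, and the pooled factor at a 20% share is 1.02. With d = 0.30, recorded adherence (0.822) exceeds true adherence.

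**Step 4: purely random error, as a second model.** With reliability ρ, the pooled factor is 1/(1 + f(1 − ρ)/ρ). For f = 0.20 and ρ = 0.7 this is 1/(1 + 0.2 × 0.3/0.7) = 0.92. Across shares of 10% to 50% and reliabilities of 0.9 to 0.5, it runs from 0.99 to 0.67.

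**Step 5: comparison of adherence between arms.** Only the intervention arm has reminders, calls and feedback, so omission could differ by arm. If it were higher among controls by 10 points, with mean adherence 0.8 and a 20% share, the arm difference would be inflated by 0.2 × 0.8 × 10 = 1.6 points. Nothing in the documents shows that it does differ.

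**The case against.** The plan discloses the record as indirect and gives the reason for it. The general claim about what the reports detect is introductory text on the technology, and the Ellipta-specific description comes later. No monitor here proves inhalation: one records actuation and the other removal of a capsule. Ellipta adds a second action and so a further source of error. The plan never states that the records are pooled or treated as true adherence. That is inferred from the single definition set and the absence of any split. Both the direction and the size are undetermined, and with a small Ellipta share and good compliance the effect is negligible (0.99 at 10%). The primary outcome does not use these data.

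All of this stands, and it limits the point. It does not remove it, because disclosing a proxy is not the same as analysing it as one, and a reader of the results could not tell which of the cases above applied.

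A reader might go further and infer that the Ellipta patients should leave the main adherence analyses. The documents do not support that. It would drop randomised patients from a stated aim because of an error of unknown size. Patients demonstrate technique with all their prescribed devices, so some may combine Ellipta with a monitored inhaler, and prescriptions can change during follow-up. A baseline split alone would therefore not isolate the proxy data.

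**Conclusion.** The point holds as a gap in the secondary and predictor analyses. An unvalidated proxy for one device enters adherence measures that serve a stated aim, with no separation by recording type and no check.

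A reader might infer that recorded adherence is necessarily too low and its link with exacerbation necessarily weakened. That is not supported. Attenuation is the more common result under the assumptions tried, but false puffs can cancel the drop in mean adherence and push the slope factor above 1. At an assumed 20% Ellipta share, with placebo-puff compliance of 95% to 80% and up to 20% false puffs, the pooled factor runs from about 0.74 to 1.02. The larger distortions need both a sizeable share and poor compliance, and neither is documented. These figures also assume a linear slope, no error in the other records, and the same true adherence across devices.

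Nor do the documents support reading this as a threat to the primary result: the comparison of time to exacerbation by arm uses no adherence record.

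**What to change.** In the statistical analysis section:

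1. Keep all randomised patients in the main adherence analyses.
2. Pre-specify reporting of taking adherence, timing adherence and gaps separately for the placebo-actuation record and for directly monitored devices (Smartinhaler on the treatment inhaler, and POEMS).
3. Include recording type as a term in the adherence-exacerbation model. This removes a shift in level between recording types, but not random error within the Ellipta records, so item 4 is also needed.
4. Add a sensitivity analysis that excludes patients with any Ellipta placebo record.
5. State the rule for classifying patients who use several inhalers or switch device. Switches occur after randomisation, so arm comparisons in the restricted set should be labelled accordingly.

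In the section on medication adherence, qualify the general claim about what the reports detect so that it excepts Ellipta.

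The cost is plan wording and a few extra tables from data already collected, plus lower precision in the restricted analysis, in proportion to the Ellipta share.

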initiation, implementation and persistence. The process starts with the *initiation*, characterised by the intake of the first dose of a prescribed medication by the patients. It continues with the *implementation* of the dosing regimen, which is defined as the extent to which a patient's actual dosing corresponds to the prescribed medication, from initiation until the last dose is taken. This represents a longitudinal description of patient behaviour over time. The last step of the process is the *persistence*, which is the time duration from initiation, until eventual treatment discontinuation. After discontinuation, a period of nonpersistence may follow until the end of the prescribed period.

According to the above defined processes, non-adherence to medications can occur in the following situations: late or non-initiation of the prescribed treatment, suboptimal implementation of the dosing regimen or early discontinuation of the treatment. The subdivision into individual processes helps to focus research questions and to find measures and corresponding data to answer them.

On average, adherence to long-term therapy is estimated to be around 50% as shown in a systematic review summarising the results of randomised controlled trials (RCTs) of interventions to help patients follow prescriptions for medications for medical problems[16]. In general, adherence to medication can be measured using direct or indirect methods. Direct methods include direct observation of drug intake or measurement of drug concentration respectively biologic markers in blood, urine, or other body fluids. Indirect methods include assessment of a patient's clinical response, pills count, rates of refilling prescriptions, patient's self-report, and as most recommended method the electronic monitoring[17, 18]. Currently, no method is considered to represent the gold standard for measuring adherence to medications[19, 20]. Nevertheless, the method of choice that has emerged recently is the use of electronic monitoring[21].

A review by Makela et al.[22] analysed studies about asthma and COPD adherence between 2000 and 2012. The three leading methods were self-reported measures (37.8%), prescription refill adherence (32.8%) and electronic monitoring (19.1%)[22].

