In this prospective single-blinded randomized controlled trial (RCT) (see figure 1 for study flow chart) 169 participants are followed up for six months. Prior to study start, patients have to be in a stable phase of their obstructive lung disease, which is defined as an exacerbation-free period of at least one month prior to commencement of the study and no current hospitalization for any other medical condition. Study participants will continue to be cared by their usual treating physician(s). They decide on all prescriptions and treatments.

All participants take part in a training course before the baseline visit. The goal of the training course is to provide refresher training on inhalation techniques in order to ensure that all participants are at the same level of disease knowledge and use their medication correctly. The training begins with a brief introduction about asthma and COPD. Then, the most frequently used devices are presented and briefly demonstrated. Correct technique depends on inhaler type, and it is important that patients use their own inhaler correctly. In addition, common mistakes and problems associated with the use of the devices are explained. The

correct use of the individual devices is demonstrated by a short film (produced by the “Deutsche Atemwegsliga” Bad Lippspringe, Germany)[36] which presents the most important steps to follow in order to achieve an effective inhalation. Notably, it has been shown that the manufacturer’s instruction sheet is not effective enough to achieve correct techniques[37-39]. In contrast verbal and visual instructions seem to have a higher success rate in improving the application of inhalation devices[40]. At the end of the training, participants are given the opportunity to ask questions concerning the devices.

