- Timing adherence: (Number of correct dosing intervals during 24 hours/number of dosing intervals during 24 hours) x100; correct dosing intervals are prescribed intervals $\pm 25\%$:
 - o For once daily dosing: $24h \pm 25\% = 18-30h$
 - o For twice daily dosing: $12h \pm 25\% = 9-15h$
 - o For three daily dosing: $8h \pm 25\% = 6-10h$
- Gaps: (Number of days without inhalation during the whole study period/number of days in same time period) x 100.
- Maximal gap length: Number of consecutive days of the longest period of time without inhalation.

Different lung function tests are performed at baseline, after two, four and six months to assess changes in lung function (FEV₁, FVC, FEV₁/FVC), diffusion capacity, NO-measurements and CO-measurements.

To evaluate the inhalation technique, participants demonstrate at baseline and at every follow up visit how they actually use their device at home. For this purpose, placebo devices are used to prevent overdosing. Correctness of inhaler use is assessed using pre-defined checklists for each inhaler type based on user guidelines and instruction package inserts from the manufacturers[50-55]. Correct inhaler usage is defined as correct performance of every step on the checklist. Incorrect inhaler usage is defined as one or more steps done incorrectly. A total score is calculated (incorrect application =0, correct application =1) and applied to every step. Possible errors are corrected by verbal instruction and visual demonstration. For ethical reasons the correction was performed in both groups. Patients demonstrate their inhalation technique until it is performed correctly.

To assess patients' beliefs about the need of the prescribed medication and their concerns about the potential adverse consequences of taking it, the BMQ is used at baseline.

Changes in quality of life are assessed at baseline, after two, four, six months using different disease-specific questionnaires: SGRQ, CAT and ACT. To assess general quality of life, SF-36-questionnaire is used.

STATISTICAL ANALYSIS

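### Gaps is presented as an implementation measure but is computed over the whole study period, so days after an inhaler has been stopped count as poor implementation

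*Combined protocol and SAP*

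**What the plan says.** The Medication Adherence section of the introduction adopts a taxonomy with three components. Implementation is "the extent to which a patient's actual dosing corresponds to the prescribed medication, from initiation until the last dose is taken". Persistence is a separate component, "which is the time duration from initiation, until eventual treatment discontinuation". The days that follow are placed outside implementation: "After discontinuation, a period of nonpersistence may follow until the end of the prescribed period". The same section lists "suboptimal implementation of the dosing regimen or early discontinuation of the treatment" as different ways of being non-adherent.

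Data Collection and Outcome Measures then chooses one component: "This project focuses on the implementation of a prescribed dosing regimen". Four measures follow:

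- Taking adherence and timing adherence are each defined per 24 hours.
- Gaps is the percentage of days with no inhalation, with the entire study as the window in both numerator and denominator.
- Maximal gap length is "Number of consecutive days of the longest period of time without inhalation", with no window given.

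Four other places bear on the point. Measurement of Objective Adherence has recording run from T0 to T3. Study Design and Procedures leaves treatment to the usual physicians: "They decide on all prescriptions and treatments". Statistical Analysis lists gaps, with taking and timing adherence, as predictors of time to exacerbation. Handling of Missing Data and Drop Outs covers patients who leave the study, but not patients who stop an inhaler and stay in follow-up.

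**The concern.** By its written definition, Gaps includes days that the protocol's own taxonomy assigns to non-persistence. A patient who skips every third day and a patient who takes every dose and then stops for good can have the same Gaps value. The plan labels both as poor implementation.

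The denominator is calendar days, not days on which inhaled medication was prescribed. A patient whose physician has stopped the inhaler therefore accrues gap days while following the prescription exactly.

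Two readings of the results are at stake. First, a difference between arms in Gaps could come from fewer missed doses, fewer patients stopping, or different prescribing, and the planned summary does not separate them. The intervention could act on more than one of these: reminders address each dose, and the support call is triggered by a run of days off schedule, which someone who has stopped would also meet. Second, where Gaps is a predictor of exacerbation, missed doses and stopping share one coefficient.

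**Working it through.** The plan states no figure for this point, so there is none to reproduce. The check compares windows and then illustrates the size.

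**Windows side by side**

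| Item | Window | Where |
|---|---|---|
| Implementation | first dose to last dose taken | Medication Adherence |
| Time after stopping | non-persistence | Medication Adherence |
| Gaps | entire study, stated | Data Collection and Outcome Measures |
| Maximal gap length | not stated; T0 to T3 inferred from the recording period | Data Collection and Outcome Measures; Measurement of Objective Adherence |
| Taking, timing | per 24 hours; days to be summarised not stated | Data Collection and Outcome Measures |

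The mismatch is explicit for Gaps and inferred for maximal gap length. No section defines discontinuation or a stop date, and current medication is listed only among the baseline data.

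**Size in one patient**

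Inputs: six months of follow-up (Study Design and Procedures), taken as D = 183 days. Assumptions: once-daily dosing, last dose on day L, m missed days before L, and the patient stays in the study.

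- Whole-period Gaps = (m + D − L)/D
- Gaps to last dose = m/L

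Perfect use, stop at L = 61: (0 + 122)/183 = 66.7%, against 0/61 = 0%. The maximal gap is 122 days, against 0.

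With about 5% of days missed while on treatment (m rounded):

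| L | m | Whole-period Gaps | Gaps to last dose | Final silent run |
|---|---|---|---|---|
| 30 | 2 | 155/183 = 84.7% | 2/30 = 6.7% | 153 days |
| 61 | 3 | 125/183 = 68.3% | 3/61 = 4.9% | 122 days |
| 91 | 5 | 97/183 = 53.0% | 5/91 = 5.5% | 92 days |
| 122 | 6 | 67/183 = 36.6% | 6/122 = 4.9% | 61 days |
| 152 | 8 | 39/183 = 21.3% | 8/152 = 5.3% | 31 days |
| 183 (no stop) | 9 | 9/183 = 4.9% | 9/183 = 4.9% | none |

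For everyone who stops, most of the whole-period score is time after the last dose.

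**Size in an arm**

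Calculation of Sample Size gives 70 + 7 = 77 per arm. If k patients with perfect use stop on day 61, the arm mean rises by k/77 × 66.7 percentage points:

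- k = 2: 1.7 points
- k = 5: 4.3 points
- k = 10: 8.7 points

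The documents give no stopping rate, so k is an assumption. Equal numbers stopping at equal times in both arms would leave the between-arm difference unchanged.

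**The case against.** The strongest reply is that whole-period Gaps is a sound measure with an imprecise label. It keeps every randomised patient on the same window. Cutting at the last dose conditions on something that happens after randomisation: a patient who is perfect for five days and then stops would score 0% gaps. The last recorded dose is also a weak marker of stopping. POEMS data are read only when the card comes back, and Ellipta use is recorded only if the patient also triggers a placebo device. All of this stands, and it is why the whole-period figure should be kept and not replaced.

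A second reply is that having no persistence outcome is a choice of scope, since the protocol declares an implementation focus. That is partly fair. It does not explain why a measure under that focus counts days outside it.

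A third reply is that reminders, calls and feedback are tested as one package and no objective separates missed doses from stopping. That is also true. It limits the consequence to how Gaps is labelled and interpreted.

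A reader might further infer that a switch to another inhaler is scored as a gap to month six. The documents do not say so. Gaps counts days without inhalation, not days on which the original device is silent, and a patient moved to another monitored inhaler still records inhalations. The handling of switches is simply unstated.

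**Conclusion.** The point holds as a mismatch between the declared construct and the definition of one secondary measure. Gaps, by its stated window, scores days after stopping as poor implementation, including stops ordered by the prescriber. Maximal gap length does the same if, as seems natural, its window is T0 to T3. Nothing elsewhere in the plan repairs this.

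For one patient the effect can be large: 66.7% against 0% for a perfect user who stops on day 61. For an arm it depends on how many patients stop while remaining in the study, which is unknown. No bias between arms has been shown.

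A reader might infer that the trial cannot say anything about implementation. That goes too far. Taking and timing adherence are defined per 24 hours and do not carry the whole-period wording. The time-stamped records would also allow a later separation; it is just not pre-specified. The Study Objective speaks of adherence in general. The primary between-arm comparison of time to exacerbation does not use Gaps and is unaffected, although the planned predictor analysis does use it. The change is worth making before analysis, so that the window is not chosen after the data have been seen.

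**What to change.** 1. Keep whole-period Gaps and maximal gap length as the between-arm measures on a common window, state T0 to T3 for both, and label them overall adherence (implementation plus persistence).
2. Record prescriber stop and switch dates at each visit. Remove days with no inhaled medication prescribed from numerator and denominator. Count inhalations from the currently prescribed device, so that a switch is not read as a gap.
3. Add as supportive analyses: Gaps and maximal gap length from T0 to the last recorded dose (implementation), and time from T0 to last dose by arm (persistence), with prescriber stops identified separately.
4. Pre-specify when silence counts as discontinuation. Treat unreturned POEMS cards and missing device data as missing, not as stopping.
5. State which days enter the summaries of taking and timing adherence, and which version of Gaps is the predictor in the exacerbation model.

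The cost is analysis wording and one data field per visit. The study is already under way, so stop and switch dates for patients who have finished would have to be obtained retrospectively, for example from the treating physician, whom the plan already contacts when a patient cannot date an exacerbation. The main downside is that the last-dose measures compare arms over unequal windows set after randomisation, so they must be read together with the whole-period figure and not alone.
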